## 5.0 Subject Disposition

The number of subjects for each of the following categories will be summarized overall and by treatment groups in the ITT 1 Population:

- Subjects randomized
- Subjects randomized and took at least one dose of study drug in Period 1
- Subjects who completed Period 1
- Subjects who completed study drug in Period 1
- Subjects who prematurely discontinued study in Period 1 (all reasons and primary reason)

- Subjects who prematurely discontinued study drug in Period 1 (all reasons and primary reason)
- Subjects who were rescued in Period 1
- Subjects who experienced dose escalation to upadacitinib 30 mg in Period 1

The summary will be provided for Period 2 for each of the following categories for overall and by treatment group in the ITT 2 Population:

- Subjects who enter Period 2
- Subjects who took at least one dose of study drug in Period 2
- Subjects who complete Period 2
- Subjects who complete study drug in Period 2
- Subjects who prematurely discontinue study in Period 2 (all reasons and primary reason)
- Subjects who prematurely discontinue study drug in Period 2 (all reasons and primary reason)
- Subjects who were rescued in Period 2
- Subjects who received dupilumab at Baseline and experienced dose escalation to upadacitinib 30 mg in Period 2

## 6.0 Study Treatment Duration and Compliance

For Period 1 and Period 2, the duration of treatment will be summarized by treatment groups using the Safety 1 and Safety 2 Populations, respectively.

### **Study Drug Duration (in Days) in Period 1:**

Duration of upadacitinib in Period 1 is defined for each subject as

- For subjects who do not continue into Period 2:  
Date of the last dose of study drug in the Period 1 - Date of the first dose of study drug in Period 1 + 1

- For subjects who continue into Period 2:  
Minimum of (Date of the first dose of study drug in Period 2 - Date of first dose of study drug in Period 1, Date of the last dose of study drug in Period 1 - Date of first dose of study drug in Period 1 + 1)

Duration of upadacitinib 15mg for subjects who have never experienced dose escalation in Period 1 is defined as

- Date of the last dose of upadacitinib 15 mg in the Period 1 - Date of the first dose of upadacitinib 15 mg in Period 1 + 1

Duration of dupilumab in Period 1 is defined for each subject as

- For subjects who do not continue into Period 2:  
Last dose date of dupilumab in Period 1 - first dose date of dupilumab in Period 1 +14
- For subjects who continue into Period 2:  
Minimum of (Date of the first dose of upadacitinib in Period 2 - Date of first dose of dupilumab in Period 1, Date of last dose dupilumab in Period 1 - Date of first dose of dupilumab in Period 1 + 14)

### **Study Drug Duration (in Days) in Period 2:**

Duration of upadacitinib in Period 2 is defined for each subject as Date of the last dose of study drug in the Period 2 - Date of the first dose of study drug in Period 2 + 1.

### **During the administration of upadacitinib (applicable for All UPA Population only):**

Duration of upadacitinib is defined for each subject as the last dose date of upadacitinib - first dose date of upadacitinib +1.

Duration of treatment will be summarized using the number of subjects treated, mean, standard deviation, median, minimum, and maximum. In addition, the number and percentage of subjects in each treatment duration intervals will be summarized:

- ( $\geq 4$  weeks,  $\geq 8$  weeks,  $\geq 16$  weeks) for Period 1
- ( $\geq 4$  weeks,  $\geq 16$  weeks) for Period 2
- ( $\geq 4$  weeks,  $\geq 8$  weeks,  $\geq 16$  weeks,  $\geq 20$  weeks, and  $\geq 32$  weeks) for All UPA Population

**Compliance:**

Treatment compliance will be summarized

- In Period 1 for Safety 1 Population
- In Period 2 for Safety 2 Population
- During the administration of upadacitinib for All UPA Population

Upadacitinib compliance is defined as the number of upadacitinib tablets actually taken (i.e., the difference between the number of tablets dispensed and the number of tablets returned) by the subject divided by the number of tablets planned to be taken by the subject in Period 1, Period 2 and during the administration of upadacitinib (for All UPA Population), respectively.

The planned tablets for upadacitinib defined as follows:

**In Period 1:**

- For subjects who took UPA 15 mg QD, then escalate dose to UPA 30 mg QD in Period 1, the number of planned tablets for UPA 15 mg QD will be used before dose escalation; the number of planned tablets for UPA 30 mg QD will be used after dose escalation, and the number of planned tablets of UPA 30 mg QD depends on the tablet types (15 mg or 30 mg depends on the site).
- For subjects who took UPA 15 mg QD and never received UPA 30 mg QD in Period 1, the number of planned tablets for UPA 15 mg QD will be used.

### **In Period 2:**

- For subjects who took UPA 15 mg QD in Period 1, then took dose to UPA 30 mg QD in Period 2, the number of planned tablets for UPA 30 mg QD will be used in Period 2, and the number of planned tablets of UPA 30 mg QD depends on the tablet types (15 mg or 30 mg depends on the site).
- For subjects who took dupilumab in Period 1, then took UPA 15 mg QD and never experience dose escalation in Period 2, the number of planned tablets for UPA 15 mg QD will be used in Period 2.
- For subjects who took dupilumab in Period 1, switched to UPA 15 mg QD at the beginning of Period 2 and then escalated dose to UPA 30 mg QD, the number of planned tablets for UPA 15 mg QD in Period 2 will be used before dose escalation; the number of planned tablets for UPA 30 mg QD in Period 2 will be used after dose escalation, and the number of planned tablets of UPA 30 mg QD depends on the tablet types (15 mg or 30 mg depends on the site).

### **During the administration of upadacitinib for All UPA Population:**

- For subjects who took UPA 15 mg QD, then escalate dose to UPA 30 mg QD, the number of planned tablets for UPA 15 mg QD will be used before dose escalation; the number of planned tablets for UPA 30 mg QD will be used after dose escalation, and the number of planned tablets of UPA 30 mg QD depends on the tablet types (15 mg or 30 mg depends on the site).
- For subjects who took UPA 15 mg QD and never experienced dose escalation, the number of planned tablets for UPA 15 mg QD will be used.

Dupilumab compliance is defined as the number of dupilumab injections administered during the subject's participation divided by the number of injections planned during the subject's participation in Period 1. The number of injections planned for dupilumab group in Period 1 is based on protocol Amendment 2.0, i.e., Week 14 dupilumab dose will be the last planned dose for all subjects in the dupilumab group if they complete Period 1.

## 7.0 Subject Characteristics

### 7.1 Demographics and Baseline Characteristics

The following demographic and baseline characteristics will be summarized for each treatment and overall in each ITT Population.

#### **Demographics:**

- Sex (female, male)
- Age (years)
- Age categories 1 (12 to < 18; 18 to < 40;  $\geq$  40 to < 64 years).
- Age categories 2 (< 18 years,  $\geq$  18 years)
- Race (White, Black or African American, Asian, American Indian/Alaska Native, Native Hawaiian or Other Pacific Islander, Other, Multiple)
- Ethnicity (Hispanic or Latino, Not Hispanic or Latino)
- Body Weight (kg)
- Height (cm) for adolescents
- Body Mass Index (BMI) ( $\text{kg}/\text{m}^2$ ) for adolescents and overall
- BMI categories (< 25  $\text{kg}/\text{m}^2$ ,  $\geq$  25  $\text{kg}/\text{m}^2$  to < 30  $\text{kg}/\text{m}^2$ ,  $\geq$  30  $\text{kg}/\text{m}^2$ ) for adolescents and overall
- Tobacco/Nicotine and Alcohol Use:
  - Tobacco/Nicotine Use (unknown, never, current, former)
  - Alcohol Use (unknown, never, current, former)

#### **Baseline Characteristics**

- Baseline EASI (< median,  $\geq$  median)
- Body Surface Area (BSA) in percentage
- Baseline vIGA-AD (3, 4)
- Previous systemic therapy (with and without)
- EASI overall score and body region scores

- Worst Pruritus NRS (Weekly Average)
- Prior Atopic Dermatitis Treatment
- Disease duration since diagnosis (years)
- Disease duration since symptoms started (years)
- Duration between symptoms and diagnosis (years)

### **Clinical Test at Screening**

- TB Status: Tuberculin PPD skin test result, QuantiFERON-TB Gold test result, Latent TB (Yes/No)
- Hepatitis B Virus (HBV)/Hepatitis C Virus (HCV)
- Chest x-ray
  - Normal, Abnormal
  - Calcified granulomas (Absent, Present)
  - Pleural scarring (Absent, Present)
  - Pleural thickening (Absent, Present)
  - Indicative of previous TB infection (Yes, No)

## **7.2 Medical History and Prior and Concomitant Medications**

Medical history data will be coded using the Medical Dictionary for Regulatory Activities (MedDRA). The actual version of the MedDRA coding dictionary will be noted in the statistical tables and clinical study report. The number and percentage of subjects in each medical history category (by MedDRA system organ class (SOC) and preferred term) will be summarized overall and by treatment group for the safety Populations. The SOC will be presented in alphabetical order, and the preferred terms will be presented in alphabetical order within each SOC. Subjects reporting more than one condition/diagnosis will be counted only once in each row (SOC or preferred term).

A prior medication is defined as any medication taken prior to the date of the first dose of study drug. Prior medications will be summarized in the Safety Populations.

- A concomitant medication in Period 1 is defined as any medication that started prior to the date of the first dose of study drug in Period 1 and continued to be taken after the first dose of study drug in Period 1; or any medications taken after the first dose of study drug and within 1 day of the last dose of study drug for the subjects on upadacitinib in Period 1, and within 14 days of the last dose of study drug for the subjects on dupilumab in Period 1, respectively.
- A concomitant medication in Period 2 is defined as any medication that started prior to the date of the first dose of study drug in Period 2 and continued to be taken after the first dose of study drug in Period 2 or any medications, other than study drug, taken after the first dose of study drug and within 1 day of the last dose of study drug in Period 2.

Concomitant medications will be summarized by periods in each Safety Population. Prior medications will be summarized in the Safety Populations. The number and percentage of subjects taking medications will be summarized by generic drug name based on the World Health Organization (WHO) Drug Dictionary for both prior and concomitant medications.

### **7.3 Protocol Deviations**

Protocol deviations include eligibility criteria violations, receipt of wrong treatment or incorrect dose of study treatment, development of withdrawal criteria without being withdrawn, and use of prohibited concomitant medications. A listing of subjects with protocol deviations will be provided.

For each of the following protocol deviation categories and across all categories, the number and percentage of randomized subjects with at least one protocol deviation will be summarized overall and by treatment group in the ITT 1 and ITT 2 Populations:

- Subject entered the study even though she/he did not satisfy entry criteria, by entry criteria.
- Subject developed withdrawal criteria during the study but was not withdrawn.
- Subject received wrong treatment or incorrect dose of study treatment.
- Subject took prohibited concomitant medication.

## **8.0 Handling of Potential Intercurrent Events for the Primary and Secondary Endpoints**

All efficacy endpoints (defined in Section 3.1, Section 3.2, and Section 3.3) will be analyzed based on the ITT 1 Population in Period 1 and ITT 2 Population in Period 2.

The following combined composite variable strategy and treatment policy strategy intercurrent events (ICEs) handling method will be used as the primary approach to handle intercurrent events in this study for all efficacy endpoints:

Subjects will be considered as non-responders after the initiation of rescue medication (composite variable strategy); and the value for the variable of interest is used regardless of treatment discontinuation (treatment policy strategy)

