3 OBJECTIVES AND ENDPOINTS

3.1 Objectives, Hypotheses, and Estimands

Objectives

Primary

The primary study objective, related to Study Period 1, is to assess the efficacy and safety of upadacitinib, initiated at 15 mg once daily (QD) and dose adjusted based on clinical response, compared with dupilumab as per its label.

An additional objective, related to Study Period 2, is to assess the efficacy and safety of upadacitinib, initiated at 15 mg QD and dose adjusted based on clinical response, in subjects with inadequate response to dupilumab.

The primary efficacy objective is based on the achievement of a composite endpoint of at least a 90% reduction in EASI from baseline (EASI 90) and a Worst Pruritus Numerical Rating Scale of 0 or 1 (WP-NRS 0/1) at Week 16 with the treatment of upadacitinib compared with dupilumab per its label in the Intent-to-Treat (ITT) Population, which consists of all randomized subjects (Section 7.2).

Secondary

The secondary efficacy objectives are based on ranked secondary endpoints as defined in Section 3.3 with the treatment of upadacitinib compared with dupilumab in the ITT Population.

Hypotheses and Estimands for the Primary and Ranked Secondary Endpoints

The hypothesis corresponding to the primary efficacy endpoint (Section 3.2) is:

- The proportion of subjects achieving both EASI 90 and WP-NRS 0/1 at Week 16 in those treated with upadacitinib is greater than those treated with dupilumab.

The estimand corresponding to the primary endpoint is defined using the composite variable strategy, as follows:

- Difference in the proportion of subjects achieving both EASI 90 and WP-NRS 0/1 at Week 16 without the use of rescue medication, regardless of treatment discontinuation, between upadacitinib and dupilumab in the adolescent and adult subjects with moderate to severe AD who have inadequate response to systemic therapy.

The hypotheses and estimands corresponding to the ranked secondary endpoints are summarized below.

- Hypotheses: the proportion of subjects achieving each ranked endpoint in those treated with upadacitinib is greater than those treated with dupilumab

- Estimands: Difference in proportion of subjects achieving each of ranked secondary endpoints without the use of rescue medication, regardless of treatment discontinuation, between upadacitinib and dupilumab in the adolescent and adult subjects with moderate to severe AD who have inadequate response to systemic therapy.

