If the live herpes zoster vaccine is to be administered (at least 30 days [or longer if required locally] before first dose of study drug), and there is no known history of primary varicella infection (chicken pox), preexisting immunity to varicella should be confirmed with antibody testing at or prior to Screening and prior to administration of the herpes zoster vaccine. If screening varicella antibody testing is negative, the live herpes zoster vaccine should not be administered.

For Japan only: In Japan, it is recommended that the live herpes zoster vaccine be considered for administration at least 8 weeks before the first dose of study drug in subjects greater than 50 years of age.

Administration of inactivated (non-live) vaccines is permitted prior to or during the study according to local practice guidelines. Examples of common vaccines that are inactivated, toxoid or biosynthetic include, but are not limited to, injectable influenza vaccine, pneumococcal, Shingrix (zoster vaccine, recombinant, adjuvanted), pertussis (Tdap) vaccines and SARS-CoV-2 (inactivated, mRNA, RNA) vaccines. Whenever possible, subjects should not have received a COVID-19 vaccination in the 7 days prior to randomization or plan to receive a COVID-19 vaccination within the first 7 days after initiation of study drug. Viral vector vaccines that are not of replicating potential (such as Convidecia and Convidecia Air to treat Covid-19) are allowed.

Rescue Concomitant Medications and Therapy

Period 1

Upadacitinib arm: Starting four weeks following dose escalation to upadacitinib 30 mg QD in Period 1, subjects with a < EASI 50 response or < 4-point improvement from Baseline in WP-NRS (weekly average) will have the option to add topical therapy (except for topical JAK inhibitors) as rescue therapy.

Dupilumab arm: Starting at Week 4 of Period 1 with dupilumab as per its label, subjects with a < EASI 50 response or < 4-point improvement from Baseline in WP-NRS (weekly average), will have the option to add topical therapy (except for topical JAK inhibitors) as rescue therapy.

Period 2

Starting four weeks following dose escalation to upadacitinib 30 mg QD in Period 2, subjects with a < EASI 75 response from Baseline or < 4-point improvement from Baseline in WP-NRS (weekly average) will have the option to add topical therapy (except for topical JAK inhibitors) as rescue therapy.

All Periods

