Investigators should attempt to limit the first step of rescue therapy to topical medications and escalate to systemic medications only for those subjects who do not respond adequately after at least 7 days of topical treatment. Subjects who receive topical rescue treatment during the study treatment period can continue study drug. If a subject needs rescue treatment with a systemic agent (including but not limited to corticosteroids, cyclosporine, methotrexate, mycophenolate mofetil, azathioprine, biologics) or phototherapy, study drug should be permanently discontinued prior to the initiation of rescue systemic agent or phototherapy and subject should be discontinued from the study.

Efficacy and safety assessments should be conducted (e.g., disease severity scores, safety labs) before administering any rescue treatment. An unscheduled visit may be used for this purpose if necessary.

If there are any questions regarding concomitant or prior therapies, the AbbVie TA SD should be contacted who will then discuss it with the AbbVie Therapeutic Area Medical Director (TA MD) and provide a recommendation.

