## **9.2 Handling of Missing Data**

In Period 1, missing values and visits after the rescue will be handled by non-responder imputation (NRI) except for missing values due to COVID-19 or any other missing data that can be reasonably assumed to be Missing at Random, which will be handled by multiple imputation (NRI-MI).

- The NRI-MI will categorize any subject who does not have an evaluation during a pre-specified visit window (either due to missing assessment or due to early withdrawal from the study) as a non-responder for the visit. The only exceptions are: 1) when the subject is a responder both before and after the visit window, the subject will be categorized as a responder for the visit. 2) missing data due to COVID-19 infection or logistical restriction or any other missing data that can be reasonably assumed to be Missing at Random, will be handled by Multiple Imputation. In addition, all assessments after the start of rescue medications will not be included in the analyses; as a result, subjects will be counted as non-responders thereafter and will not be imputed by MI. Random seeds are provided in [Appendix D](#). NRI-MI is the primary approach to handle missing data for categorical endpoints in Period 1.
- Non-responder Imputation (NRI): NRI will be performed in the same way as NRI-MI without the exception #2 above. That is, missing due to COVID-19 infection or logistical restriction or any other missing data that can be reasonably assumed to be Missing at Random, will also be counted as non-responders. The NRI is a missing data handling method in a sensitivity analysis for the primary endpoint.

Subjects whose change/percent change from Baseline cannot be calculated because of a missing Baseline will be considered as a non-responder at all post-baseline visits in both NRI-MI and NRI approaches.

Multiple Imputation (MI): another missing data handling method performed in a sensitivity analysis for the primary endpoint. Markov Chain Monte Carlo (MCMC) will be first applied to augment data into monotonic missing pattern and PROC MI will be used to generate 30 datasets using the regression method.

- The imputation is done in two steps for the primary endpoint.
- Step 1: The EASI 90 and WP-NRS 0/1 (based on weekly average) are imputed separately.

For example, for EASI 90, the variables to be included in the imputation model are treatment group, major stratum (vIGA-AD categories and age),

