## **Appendix F. Rescue Definition**

The topical and systemic medications for AD therapy are coded to the following drug classes. Among these AD medications, the potential AD rescue medications are determined through a medical review process.

1. Plain Topical Corticosteroids
2. High Potency Topical Corticosteroids
3. Medium Potency Topical Corticosteroids
4. Low Potency Topical Corticosteroids
5. Topical Calcineurin Inhibitor Therapy
6. Other Topical therapy (not including moisturizers/emollients)

Concomitant medications that are categorized as "potential AD rescue" per medical review AND in categories 1 - 6 above are considered as rescue medications in Period 1 and Period 2.

The medical review process is documented in the Rescue Medication Medical Review Process - Upadacitinib AD.

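### The SAP's rescue rule covers both periods and has no reset at Week 16, so read literally it scores anyone rescued in Period 1 as a Period 2 non-responder

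*SAP*

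**What the plan says.** SAP 8.0 states the scoring rule: "Subjects will be considered as non-responders after the initiation of rescue medication (composite variable strategy". It presents this as a combined strategy whose "handling method will be used as the primary approach to handle intercurrent events in this study for all efficacy endpoints". The endpoints named are those of SAP 3.1 to 3.3, and they "will be analyzed based on the ITT 1 Population in Period 1 and ITT 2 Population in Period 2". SAP 3.3 contains the Week 32 endpoints, so the rule reaches Period 2.

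Protocol 5.4 opens topical rescue early in the comparator arm: "Dupilumab arm: Starting at Week 4 of Period 1 with dupilumab as per its label, subjects with a < EASI 50 response", or with less than a 4-point itch improvement, may add it. It also says: "Subjects who receive topical rescue treatment during the study treatment period can continue study drug". A rescued dupilumab subject can therefore reach Week 16 and, if below EASI 75, be offered upadacitinib in Period 2 (Protocol 4.1, SAP 2.3).

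SAP Appendix F gives a single definition, under which the listed topical classes that pass medical review "are considered as rescue medications in Period 1 and Period 2". It draws no boundary between the periods.

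The additional objective in Protocol 3.1 is to assess upadacitinib "in subjects with inadequate response to dupilumab".

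**The concern.** The rule has a start (first rescue) and no end. For Period 1 that is a normal composite strategy: treatment is as randomized, and needing rescue counts as failure of that treatment. For Period 2 it breaks down in the Dupilumab/Upadacitinib group, because the drug changes at Week 16. A subject who used a topical at Week 5 on dupilumab, stopped it, and then cleared on upadacitinib would stay in the Week 32 denominator and could never enter the numerator.

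These subjects belong to the population that the Period 2 objective is about. If the literal rule is programmed, the main efficacy estimate for that objective partly measures how often topicals were used on the previous drug. If a period-specific rule is programmed instead, the same data give a different rate. The SAP does not settle which is intended.

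**Working it through.** **Step 1. What bears on the Period 2 scoring.**

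- SAP 8.0: the scoring rule. It covers all efficacy endpoints in ITT 1 and ITT 2, is open-ended, and has no reset.
- SAP 9.2, NRI-MI bullet: after rescue, "subjects will be counted as non-responders thereafter and will not be imputed by MI". This wording is also open-ended, but it stands under the Period 1 rules.
- SAP 9.2, Observed Cases (OC) bullet, the Period 2 method: says nothing about rescue.
- SAP 5.0: counts subjects rescued in Period 1 and in Period 2 separately.
- SAP 7.2: defines concomitant medication by period. A medication begun earlier counts for Period 2 only if it is still taken after the first Period 2 dose.
- SAP Appendix F: builds rescue from concomitant medications, without citing the 7.2 definitions.

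This leaves two workable implementations. *Carry-forward* (8.0 as written): Period 1 rescue means non-response at Weeks 20 and 32. *Period-specific* (7.2 and Appendix F read together): only rescue used on or after the first Period 2 dose counts.

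**Step 2. Who is affected.** Dupilumab rescue opens at Week 4. Upadacitinib rescue opens four weeks after escalation, and escalation starts at Week 4, so the earliest is Week 4 + 4 = Week 8. Both Period 2 groups can contain subjects rescued in Period 1. Only in Dupilumab/Upadacitinib does the drug differ before and after Week 16.

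**Step 3. Size.** The plan gives no figure for this point, so there is none to reproduce. In the Dupilumab/Upadacitinib group let

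- r = share rescued in Period 1,
- pR = observed Week 32 response rate in those subjects,
- pN = rate in the others.

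If no one rescued in Period 1 uses rescue after the switch:

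- Carry-forward reports (1 − r) × pN.
- Period-specific reports (1 − r) × pN + r × pR.
- The shortfall is r × pR.

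Subjects who do use rescue on or after the first Period 2 dose are non-responders under both readings. They add nothing to the shortfall.

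The documents give neither r, pR nor pN. All values below are assumptions.

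| r | Carry-forward rate if pR = pN = 60% | Shortfall, pR = 40% | pR = 60% | pR = 80% |
|---|---|---|---|---|
| 10% | 54% | 4 | 6 | 8 |
| 20% | 48% | 8 | 12 | 16 |
| 30% | 42% | 12 | 18 | 24 |
| 40% | 36% | 16 | 24 | 32 |

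Shortfalls are in percentage points; for example, 0.30 × 0.60 = 0.18.

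**Step 4. Would the interval show it?** Take an assumed 150 entrants, r = 30% and pR = pN = 60%. The carry-forward rate is 0.70 × 0.60 = 42%. Its 95% interval is 0.42 ± 1.96 × √(0.42 × 0.58 / 150), about 34% to 50%, which excludes the 60% actually observed.

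**Step 5. Why the OC rule must be named.** If post-rescue values were instead dropped as unavailable under OC, the reported rate would be pN. With r = 40%, pR = 40% and pN = 60%, carry-forward gives 36%, period-specific gives 0.36 + 0.16 = 52%, and dropping gives 60%. One data set yields three rates.

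**The case against.** The strongest reply is that the SAP already treats rescue by period. Disposition counts it by period, concomitant medication is defined by period, the explicit open-ended sentence sits in the Period 1 bullet, and the Period 2 OC rule does not mention rescue. Appendix F makes rescue a subset of concomitant medications. Read with 7.2, a topical stopped before the switch is then not a Period 2 rescue, and one continued past it is.

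Much of this stands. A reader might infer from 8.0 that the sponsor has decided to score dupilumab subjects rescued in Period 1 as upadacitinib failures throughout Period 2. The documents do not support that: no section says Period 1 rescue carries over. But none of the sections above is the scoring rule, none overrides 8.0, and Appendix F does not link to 7.2. They show that another reading is available, not that it is the one specified.

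Four further points are fair:

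- The literal rule also marks upadacitinib-arm subjects rescued in Period 1, so it is not confined to the dupilumab arm.
- Rescue is optional, and the itch criterion alone permits it. The documents therefore do not show that rescued dupilumab subjects are mostly those below EASI 75 at Week 16, or how many enter Period 2.
- No between-group test is planned in Period 2, and both groups are selected on Week 16 response, so little should be made of distortion between them.
- Counting any rescue used on or after the first Period 2 dose still makes a non-responder of a subject whose dupilumab-era topical ran a few days past the switch. That residue is real. It is why carry-over cases should be shown separately.

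**Conclusion.** The point holds as a defect in a stated rule. Followed as written, SAP 8.0 gives a Period 2 estimate that does not answer the Period 2 objective. The sections that suggest a better reading do not establish it.

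The shortfall under the literal reading is r × pR, about 4 to 32 points for assumed r of 10–40% and pR of 40–80%. It is zero only if no entrant was rescued in Period 1, or if none of those rescued would count as a responder. The range shows what the choice of reading could do; it is not an established bias, because both inputs are assumed and it applies to one reading only.

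A reader might also suspect that the main result is at risk. It is not: Period 2 efficacy is descriptive and its endpoints lie outside the ranked hierarchy, so the primary and ranked tests and the type I error are untouched. This should be corrected, but it does not threaten the trial's primary conclusion.

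**What to change.** In SAP 8.0, Table 2 and Appendix F, state that:

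- for Period 2 endpoints, the intercurrent event is rescue medication used on or after the first Period 2 dose, in line with the Period 2 concomitant-medication definition in SAP 7.2;
- rescue that ended before that dose does not make a subject a Period 2 non-responder;
- the rule applies within the OC analysis and to both Period 2 groups.

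Report, by group, how many Period 2 entrants were rescued in Period 1. Show the Week 32 results under carry-forward as a sensitivity summary, and say how rescue that continued across Week 16 was classified.

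The cost is SAP wording, one derivation and one extra summary. Protocol 5.4 already requires start and end dates for concomitant medication. The small downside is that incomplete stop dates need a convention, which should be written down with the rule.
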